3.1. Inclusion Criteria

- 3.1.1. Patients 16 years or older with Philadelphia chromosome (Ph)- or BCR/ABL-positive CML (as determined by cytogenetics, FISH, or PCR).
- 3.1.2. Patients must have received FDA-approved TKI therapy for at least 18 months and not have increased their dose of FDA-approved TKI in the last 6 months. Patients participating on frontline protocols 2005-0048 (nilotinib) and 2005-0422 (dasatinib) are eligible for enrollment on this study.
- 3.1.3. Phase II patients must be in complete cytogenetic remission.
 - 3.1.3.1. For the phase I portion of the study, patients may be included without a complete cytogenetic remission provided they are in chronic phase
- 3.1.4. Phase II patients must have detectable BCR-ABL transcript levels meeting at least one of the following criteria:
 - 3.1.4.1. Patient has never achieved a major molecular response, and transcript levels have shown in at least two consecutive measures separated by at least 1 month to have increased by any value, or
 - 3.1.4.2. Achieved a major molecular response that has been lost with an increase in transcript levels by at least 1-log, confirmed in two consecutive analyses separated by at least 1 month, or
 - 3.1.4.3. The patient has received therapy for at least 2 years and does not have a sustained major molecular response, or
 - 3.1.4.4. The patient has received therapy for at least 5 years and does not have a sustained complete molecular response.
 - 3.1.4.5. Patients included in the phase I portion of the study are eligible regardless of their level of BCR-ABL transcripts.

- 3.1.5. Patients must not have had a known continuous interruption of imatinib therapy of greater than 14 days or for a total of 6 weeks in the 6 months prior to enrollment.
- 3.1.6. Patients must sign an informed consent indicating that they are aware of the investigational nature of this study in keeping with the policies of the hospital.
- 3.1.7. ECOG performance status ≤ 2 .
- 3.1.8. Adequate organ function defined as: bilirubin $< 2x$ upper limit of normal (ULN) (unless associated with Gilbert's syndrome), and ALT or AST $\leq 2.5x$ ULN.
- 3.1.9. ANC $\geq 1 \times 10^9/L$ and platelets $\geq 50 \times 10^9/L$.

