- 5.1.5. Peripheral blood and/or bone marrow for quantitative PCR (QPCR) (if not done within 3 months).
- 5.1.6. Peripheral blood and/or bone marrow for correlative studies (optional – Appendix A, B & C). Not all optional samples may be collected.

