5.2. Evaluation During Study

- 5.2.1. Physical exam and evaluation of toxicity (clinic visit or telephone interview):
 - 5.2.1.1. Phase I portion: every 2 weeks for the first month, then every month for the first 3 months, then every 3 months (± 1 month) until month 6, then every 6 to 12 months.
 - 5.2.1.2. Phase 2 portion: every 3 months (± 1 month) until month 6, then every 6 to 12 months.
- 5.2.2. CBC, platelet, differential every 1-2 weeks for 8 weeks, then at the start of every cycle. Differential not required if $WBC \leq 0.5 \times 10^9/L$.
- 5.2.3. Bone marrow aspirate with cytogenetics or FISH every 3-6 months in year 1, then as clinically indicated.
- 5.2.4. Total bilirubin, SGPT or SGOT, and creatinine every 1-2 weeks for 8 weeks, then before each cycle.
- 5.2.5. Quantitative PCR (peripheral blood and/or bone marrow) before each cycle for 3 cycles, then every 3-6 cycles until one year, then every 6-12 cycles.
- 5.2.6. Peripheral blood and bone marrow for correlative studies every 3-6 months in year 1, then every 6-12 months. Methylation studies will also be done on days 5, 10 and 28 (all ± 3 days) of the first cycle. Not all optional samples may be collected. (Optional – Appendix A, B & C).

6. Criteria for Response

- 6.1. A favorable response for the primary endpoint is defined as a greater than a one-log reduction of BCR-ABL transcript levels from the baseline level at the time vaccination was initiated, or a disappearance of BCR-ABL transcripts (i.e., complete molecular response).

7. Criteria for Removal from Study

- 7.1. The patient receives CML-directed therapy other than TKI and AZA.
- 7.2. The patient develops disease progression defined as confirmed loss of CCyR, confirmed loss of CHR or transformation to accelerated or blast phase.
- 7.3. The dose of TKI is increased or new therapies for their leukemia are added.
- 7.4. The patient has a continuous interruption of imatinib therapy for greater than 6 weeks.
- 7.5. The patient withdraws consent.
- 7.6. The treating physician considers it in the best interest of the patient.
- 7.7. Pregnancy or suspected pregnancy

8. Adverse Event Reporting

- 8.1. Adverse event is any untoward medical occurrence that may present during treatment with a pharmaceutical product but which does not necessarily have a causal relationship with this treatment.

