The rate of molecular response will be estimated with 95% confidence interval. The null hypothesis is that the response rate is 5%, and alternative hypothesis is that the response rate is 20%. If a 20% response is reached, the study would be considered positive. Under this setting, 36 patients can provide a power of 87% for a one-sided test of the above hypothesis at significance level $\alpha=5\%$.

10. Protocol Amendments, Deviations and Regulatory

Any amendment to this protocol must be agreed to by the Principal Investigator and by MD Anderson Cancer Center and by Celgene. Amendments should only be submitted to IRB after consideration of M. D. Anderson Cancer Center, Celgene review. Written verification of IRB approval will be obtained before any amendment is implemented.

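### The baseline PCR for the one-log response is not defined and may be the value a patient was selected on under 3.1.4.1, which biases response upward by an amount the plan does not assess

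*Combined protocol and SAP*

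**What the plan says.** - **Entry.** Section 3.1.4 offers four alternative routes: "Phase II patients must have detectable BCR-ABL transcript levels meeting at least one of the following criteria". Route 3.1.4.1 is for a patient who meets "Patient has never achieved a major molecular response" and whose "transcript levels have shown in at least two consecutive measures separated by at least 1 month to have increased by any value". No minimum rise is set. Route 3.1.4.2 also selects on a rise, but a large and confirmed one: MMR "lost with an increase in transcript levels by at least 1-log, confirmed in two consecutive analyses separated by at least 1 month". Routes 3.1.4.3 and 3.1.4.4 need no rise.
- **Pretreatment PCR.** Section 5.1.5 lists "Peripheral blood and/or bone marrow for quantitative PCR (QPCR) (if not done within 3 months"), so a recent earlier result can stand in for a new sample.
- **Response.** Section 6.1 asks for a "greater than a one-log reduction of BCR-ABL transcript levels from the baseline level", or disappearance of transcripts. It ties baseline to the start of vaccination, which is not part of this trial, and names no particular PCR. Section 9.3 counts such a fall within 12 months. Neither section asks for confirmation.
- **On-study PCR.** Section 5.2.5 schedules a PCR ahead of each of the first three cycles, then every 3 to 6 cycles to one year.
- **Test.** Section 9.1 describes a single-arm trial. Section 9.4 says "The null hypothesis is that the response rate is 5" per cent, with an alternative of 20%, and claims 87% power with 36 patients at one-sided 5%. It gives no source for the 5%.

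**The concern.** A rise of any size includes measurement noise. If a patient's true level is stable and errors are independent, the second of two measures is the higher one time in two, and three measures come out in rising order one time in six (1/3!). Section 3.1.4.1 can be read either way. In both cases the last value of the run is high partly because the patient was selected on it. If that value becomes the baseline, part of any later fall is a return to the usual level.

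In a randomised comparison both arms would share this. Here the response rate is set against a fixed 5%, so false responses count towards a positive result. Requiring confirmed responses would reduce the noise but would not correct an inflated baseline.

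**Working it through.** **1. The plan's own figure.** Exact binomial, n = 36: rejecting at 5 or more responders gives P(X≥5 | 5%) = 3.2% and P(X≥5 | 20%) = 87.3%. The stated 87% reproduces, so the design that matches it rejects at 5 of 36. Read literally, reaching an observed 20% means 8 of 36, with P(X≥8 | 5%) = 0.03% and power 43%.

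**2. Assumptions, none of them in the documents.** Stable true level; independent normal errors on the log10 scale with within-patient SD of 0.20, 0.25 or 0.30; five post-baseline looks (Section 5.2.5 allows roughly 3 to 6 in year 1); one look at least one log below baseline counts.

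**3. Lift in the baseline.** The last value of a rising pair is the larger of two draws, with mean excess 0.56 × SD. The last of a rising triple is the largest of three, with mean excess 0.85 × SD. At SD 0.30 that is 0.17 and 0.25 log, well short of one log. Selection therefore makes a chance one-log fall more likely but does not produce it alone.

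**4. False-response rate per patient.** With m = 1 (unselected), 2 (one rise) or 3 (two rises) and k = 5 looks:

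rate = ∫ m φ(b) Φ(b)^(m−1) [1 − (1 − Φ(b − 1/SD))^k] db

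| SD (log10) | unselected | one rise | two rises |
|---|---|---|---|
| 0.20 | 0.10% | 0.19% | 0.28% |
| 0.25 | 1.03% | 1.97% | 2.84% |
| 0.30 | 3.71% | 6.88% | 9.65% |

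**5. Trial-level error from selection alone.** Let d be the selected rate minus the unselected rate, and s the share of the 36 whose baseline is the selected value. Then p = 0.05 + s × 0.95 × d. At SD 0.30, d = 3.16 points (one rise) or 5.93 points (two rises).

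| s | p (one / two rises) | P(X≥5 of 36) | P(X≥8 of 36) |
|---|---|---|---|
| none | 5.0% | 3.2% | 0.03% |
| 20% | 5.6% / 6.1% | 4.9% / 6.7% | 0.1% / 0.1% |
| 50% | 6.5% / 7.8% | 8.2% / 14.7% | 0.2% / 0.6% |
| 30 of 36 (ceiling) | 7.5% / 9.7% | 13.0% / 26.8% | 0.45% / 2.0% |

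With s = 50%, P(X≥5) is 4.4% / 5.7% at SD 0.25 and about 3.4% at SD 0.20.

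**6. Likely share.** Six of the 36 come from phase I (Section 9.2.2), where 3.1.4.5 waives any transcript criterion, so at most 30 face 3.1.4. Route 3.1.4.3 admits a patient if "The patient has received therapy for at least 2 years and does not have a sustained major molecular response", which covers never-MMR patients from 2 years on without a rise. Since 3.1.2 requires 18 months of TKI, a small rise is the only way in mainly for never-MMR patients at about 18 to 24 months. The ceiling row is a bound, not a forecast.

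**7. Alternative baselines at SD 0.30.** A fresh, separate PCR returns the rate to 3.7%. The mean log10 of the three qualifying PCRs gives 0.9%, and of those three plus one fresh PCR 0.7%. If responses had to be confirmed, the rates are 1.0% with the last of two rises as baseline and 0.35% with an unselected one.

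**The case against.** The strongest reply is that the plan already implies a later baseline. Section 6.1 places it at treatment start, if vaccination is a drafting slip, and a PCR before each of the first three cycles naturally includes cycle 1. If that sample is the baseline, the selection bias is zero under independent errors. This stands as a reasonable reading, but not as a rule: 5.1.5 expressly waives a new pretreatment sample and 6.1 names none.

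The reply on size also stands in part. The SD and the route share are assumed, some rises will be real and work against a later fall, and few patients may depend on 3.1.4.1. With confirmation the selection excess at SD 0.30 is only 1.0% − 0.35% = 0.65 points per route patient.

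Three stronger readings are tempting and not supported.
- **That the false-positive rate is 26% when half enter this way at SD 0.30.** That figure comes from 0.5 × 0.05 + 0.5 × [1 − 0.95 × (1 − 0.096)] = 0.0956 and P(X≥5) = 0.258. It charges all noise to selection. Unselected noise in the same half already gives 9.3%, and the selection part alone gives 8% to 15%.
- **That the 5% null fails to allow for this.** The 5% has no stated derivation and might include background fluctuation. It can only be called unjustified.
- **That every such patient's response is partly artefact.** This holds only where the qualifying value is used as baseline and the rise was noise.

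**Conclusion.** The point holds as a gap in the baseline definition with a known direction. Following the plan as written, a value selected for being high can serve as the reference for the primary endpoint, and the bias is towards response.

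Its size is uncertain. Under the assumptions above it is negligible at SD 0.20 and modest at SD 0.25. At SD 0.30 the selection-only type I error at 5 of 36 is about 5% to 7% for a 20% share and 8% to 15% for a half share, against a nominal 3.2%. If success requires 8 of 36 it stays below 1% at those shares. The documents give neither the variability nor the share, and 3.1.4.3 and the phase I patients probably keep the share limited. The documents do not show that the trial's conclusion would be overturned. The change is still worth making because it costs little.

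**What to change.** - In Sections 6.1 and 9.3, replace the vaccination wording and define baseline as the pre-cycle-1 PCR under 5.2.5, distinct from the PCRs used for eligibility. Alternatively, use the mean log10 of that PCR and earlier PCRs of the same specimen type.
- In Section 5.1.5, state that the last qualifying PCR alone may not serve as the response baseline.
- State the basis for the 5% null and, if known, the within-patient variability of the assay.
- Report response descriptively for patients whose only qualifying criterion is 3.1.4.1 or 3.1.4.2. Restricting it to the sole criterion avoids ambiguity where a patient meets several.

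Cost: mostly wording. A patient without a fresh sample needs one drawn before cycle 1. With the averaged baseline, a patient whose transcripts are truly rising needs slightly more than a one-log fall from the latest value. Earlier PCRs can be averaged only where the specimen type matches, which the plan does not guarantee because it allows blood or marrow. A single fresh PCR removes the selection excess but not the noise from several unconfirmed looks.

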3.2. Exclusion Criteria

- 3.2.1. Patients receiving any other investigational agents
- 3.2.2. Patients who are pregnant or breast-feeding
- 3.2.3. Patients with clinically significant heart disease (NYHA Class III or IV)
- 3.2.4. Known or suspected hypersensitivity to azacitidine or mannitol.
- 3.2.5. Patients with advanced malignant hepatic tumors.

4. Treatment Plan

4.1. **TKI:** Patients will continue receiving TKI at the dose they had been receiving during the last 6 months.

4.2. **AZA:**

Phase I: patients will be treated in cohorts of 3. The starting dose will be dose level 0 (50 mg/m²/d x 3 days subcutaneous or intravenous; Table 1).

4.2.1. At least 3 patients will be entered at each level. All patients treated at any one dose level must have been observed for at least four weeks before escalating to the next dose level. Patients who come off study prior to the first four weeks and have not experienced a DLT will be replaced.

Table 1: Dose escalation levels	
Dose level	AZA (mg/m ² /d x 3 days)
-3	25 (1 day only)
-2	25 (2 days only)
-1	25
0	50
1 (Target dose)	75
2	75 (for 5 days)
3	75 (for 7 days)

4.2.2. Dose escalation will be done as follows:

Dose-limiting toxicity in	Result
0/3	Escalate to next level
1/3	Enter 3 more patients
≥2/3 or ≥ 2/6	MTD exceeded. This dose level will be declared the maximally administered dose. Expand previous level to include a total of 6 patients if not already accrued to this number.

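### Section 3.1.5 limits pre-enrolment interruption of imatinib only, although dasatinib and nilotinib patients are eligible; a transcript fall after restarting those drugs could modestly inflate the AZA response rate

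*Combined protocol and SAP*

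**What the plan says.** Section 3.1.2 requires at least 18 months of FDA-approved TKI therapy with no dose increase in the last 6 months, and adds: "Patients participating on frontline protocols 2005-0048 (nilotinib) and 2005-0422 (dasatinib) are eligible for enrollment on this study". Section 4.5.3.3 gives dose levels for imatinib, dasatinib and nilotinib.

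Section 3.1.5 then restricts earlier treatment gaps for one drug only: "Patients must not have had a known continuous interruption of imatinib therapy of greater than 14 days", or 6 weeks in total, within the 6 months before enrolment. Section 7.4, on removal from study, is also limited to imatinib.

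On study, 4.1 says: "Patients will continue receiving TKI at the dose they had been receiving during the last 6 months".

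Response under 6.1 is a fall of more than one log, or disappearance of transcripts, measured as a "reduction of BCR-ABL transcript levels from the baseline level at the time vaccination was initiated". Vaccination is not part of this trial, so I read this as the start of study treatment. Section 9.3 sets a 12-month window. Section 5.1.5 accepts a pretreatment PCR up to 3 months old, and 5.2.5 asks for "Quantitative PCR (peripheral blood and/or bone marrow) before each cycle for 3 cycles".

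Section 9.4 tests a 5% null against a 20% alternative with 36 patients, one-sided at 5%, and states 87% power. It also calls the study positive if a 20% response is reached.

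**The concern.** The limit in 3.1.5 shows that the sponsor wanted stable TKI exposure before entry. That reasoning applies equally to dasatinib and nilotinib, and the protocol gives no ground for treating them differently. A nilotinib patient off drug for 8 of the last 26 weeks is eligible; an imatinib patient with the same history is not.

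The gap matters because of the endpoint. An interruption can raise BCR-ABL transcripts and a restart can lower them whether or not AZA does anything. With no control arm, a fall after a recent restart would count as a response to the combination and be compared with a fixed 5% null. The bias runs in one direction, towards a higher apparent response rate.

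**Working it through.** **1. Does another clause close the gap?**

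- 3.1.2 bars a dose increase. A hold followed by a restart at the same dose is not an increase.
- 4.1 presumes ongoing dosing but does not bar a prior interruption.
- None of the exclusions in 3.2 concerns treatment gaps.
- 7.4 applies on study and to imatinib only.

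No clause sets a limit for the other drugs.

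**2. What reduces the risk?**

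- Phase II patients must be in CCyR (3.1.3), so transcripts cannot have risen very far.
- 3.1.4.1 and 3.1.4.2 require two consecutive measurements at least 1 month apart. This works both ways: transcripts already falling after a restart do not fit the pattern, but rises during a long hold would, and neither clause says the measurements must be the latest ones. Routes 3.1.4.3 and 3.1.4.4 need no rise.
- A baseline at treatment start removes the part of the fall before that day, but not the part after it. No minimum time since restart is set.
- A PCR before cycle 1 (5.2.5) should give a fresh baseline, but 5.1.5 lets an older pretreatment sample stand.
- The 6 phase I patients counted among the 36 (9.2.2, 9.3) lack the first two protections. They need not be in CCyR (3.1.3.1), and 3.1.4.5 says: "Patients included in the phase I portion of the study are eligible regardless of their level of BCR-ABL transcripts".

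**3. Reproducing the plan's power.** Inputs from 9.4: n = 36, null 5%, alternative 20%, one-sided 5%. By exact binomial, a cut-off of 4 responders gives a false-positive rate of 10.4%. A cut-off of 5 gives 3.24%, with power 87.3%. The stated 87% therefore corresponds to 5/36. The written 20% criterion needs 8 responders (0.20 × 36 = 7.2); its false-positive rate is 0.033%.

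**4. Size of the bias, by assumption.** The documents give neither the number of affected patients nor the chance that a restart alone produces a response. Let m of 36 patients be affected, with added chance q. Each then responds with probability 1 − 0.95(1 − q), and the rest with 0.05.

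Expected observed rate = 0.05 + 0.95·m·q/36:

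| m | q = 5% | q = 100% |
|---|---|---|
| 1 | 5.1% | 7.6% |
| 2 | 5.3% | 10.3% |

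For the false-positive rate, take the null probability of reaching the cut-off when 0, 1 or 2 patients respond from the restart for certain:

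| Cut-off | 0 certain | 1 certain | 2 certain |
|---|---|---|---|
| 5/36 | 3.24% | 9.58% | 24.07% |
| 8/36 | 0.033% | 0.15% | 0.63% |

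Weight these by the chance of each count. At 5/36:

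- m = 1: 3.24% + q × (9.58% − 3.24%). This gives 3.6% at q = 5%, 3.9% at 10%, 4.8% at 25% and 9.6% at 100%. It reaches 5% at q = (5 − 3.24)/6.34 ≈ 28%.
- m = 2: (1−q)² × 3.24% + 2q(1−q) × 9.58% + q² × 24.07%. This gives 3.9%, 4.6%, 6.9% and 24.1% at the same values of q. It reaches 5% at q ≈ 13%.

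**5. The same calculation with shares.** Let k be the share on dasatinib or nilotinib and i the share of those affected. The null rate is 0.05 + 0.95·k·i·q.

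- k = 0.5, i = 0.05, q = 0.5 (0.9 affected patients expected): null rate 6.2%, false-positive rate 6.9% at 5/36.
- k = 0.25, i = 0.02, q = 0.25: 5.1% and 3.5%.
- k = 0.75, i = 0.10, q = 1 (2.7 affected patients expected): 12.1% and 44.7%; 6.3% at 8/36.

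**The case against.** The strongest reply is that this is a drafting slip with little practical effect. Sections 3.1.2, 4.1 and 4.5.6 speak of TKI, and the reference to vaccination in 6.1 suggests text carried over from another protocol, so an all-TKI limit was probably intended. To be miscounted, a phase II patient would have to be off drug long enough for transcripts to rise by more than a log, remain in CCyR, and restart so recently that more than a log of the fall is still to come. The larger false-positive figures need one or two patients who are certain to respond from the restart; at q = 10% the rate stays below 5% even with two. The fix also leaves gaps: 3.1.5 covers only known interruptions, permits short ones, and sets no minimum time since restart for any drug.

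Most of this stands as a limit on size. It does not remove the point: 3.1.5 is an operative eligibility rule that sites and auditors apply as written, and whatever the intent, it admits the patients it was meant to exclude. The remaining gaps would be the same for all three drugs once the wording is aligned. The lack of CCyR and transcript criteria for the pooled phase I patients is a separate matter that this change does not resolve.

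**Conclusion.** The concern holds. The interruption limit covers imatinib only, eligibility covers any FDA-approved TKI, and nothing else fills the gap. The direction of bias is clear; its size is not known from the documents. With 1 or 2 affected patients, the expected upward bias in the response rate at a true 5% is 0.1–2.6 or 0.3–5.3 percentage points. The nominal 5% error at 5/36 is exceeded only if the added chance of a restart response is above about 28% (one patient) or 13% (two). Under the 20% criterion the error stays below 1%. These figures rest on assumed values of m and q and on the 5/36 cut-off inferred from the stated power; a larger number of affected patients would raise them. Because a response needs a fall of more than one log or undetectable transcripts, few patients are likely to be affected. A modest upward bias in the estimate is more likely than a changed conclusion. The wording should be corrected.

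**What to change.** In 3.1.5, replace the word imatinib with TKI, keeping the 14-day and 6-week limits and the 6-month window. Make the same replacement in 7.4, with an exception for planned TKI holds in responders, which 4.5.7.1 allows.

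The change to 3.1.5 is one word. Its cost is that a few dasatinib or nilotinib patients become ineligible, all of whom would already be excluded if they took imatinib. The sample size of 36, the exact error of 3.2% and the power of 87.3% are unchanged.
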